### **13.3 Adverse Event Relatedness**

The relatedness of the AE to the treatment device(s) and procedure(s) will be classified by the Investigator and reviewed by the Sponsor. The Investigator will use the following definitions in classifying the relationship of the AE:

- **Device Related:** AE is directly related to any CSI device used in treatment of the lesion.
- **Procedure Related:** AE is directly attributable to the index procedure.

### **13.4 Adverse Event Reporting**

Protocol reportable adverse events must be collected until each subject's completion of or exit of the study. Adverse events must be reported to the Sponsor on the AE electronic case report form (eCRF) as well as the reviewing IRB, if necessary. FDA Medical Device Reporting (MDR) requirements will be followed for this study.

## **15.0 Protocol Deviations**

A protocol deviation is defined as an event where the study is not conducted according to the protocol, FDA regulations 21 CFR Parts 50 and 56, and requirements imposed by the reviewing IRB. Protocol deviations that will be collected include, but are not limited to the following:

- Failure to obtain informed consent
- Enrolling a subject who did not meet inclusion criteria, or met exclusion criteria
- [REDACTED]

[REDACTED]

## **16.0 Site Non-Compliance**

As a result of deviation, appropriate corrective actions are to be developed by the study staff and implemented promptly. If excessive protocol deviations are noted, the Sponsor reserves the right to suspend study enrollment until a sufficient system is in place at the site to reduce further deviations, or withdraw the site from participation in the study.

## **17.0 Study Exit**

All subjects will be followed post-procedure through first standard of care follow-up visit (7-45 days post-procedure).

[REDACTED]

[REDACTED]

[REDACTED]

[REDACTED]

[REDACTED]

[figure not shown]
[REDACTED]

## **20.0 Study Termination**

The Sponsor may terminate this study at any time due to the following reasons, but not limited to: low subject recruitment/enrollment, competing studies and financial reasons. Appropriate notification will be provided to all participating Investigators.

## **21.0 Data Analysis**

Study data will be analyzed as indicated in the Statistical Analysis Plan (SAP).

## **23.0 Study Responsibilities**

### **23.1 Sponsor Responsibilities**

Sponsor responsibilities include but are not limited to:

- Selection of Principal Investigators, study sites, and Core Laboratories, if applicable, who participate in the study;
- Training of participating study sites including the Investigator and staff conducting the study;
- Providing financial support to each study site which is fair, reasonable, and equitable to fair market value;
- Following all applicable regulatory standards per applicable regulations at each study site; and,
- Ownership and control of the use of data, including review and approval of study-related publications/presentations, etc.

### **23.2 Investigator Responsibilities**

The Investigator is responsible for the following:

- Protecting the rights, safety, and welfare of subjects.
- Conducting the investigation in accordance with the Clinical Trial Agreement with the Sponsor, the Protocol, applicable FDA regulations, including 21 CFR Part 50 and 56, and any conditions of approval imposed by the IRB.
- Delegation of study-related tasks to qualified personnel under their supervision as may be applicable; however, the Principal Investigator remains responsible for the proper conduct of the clinical study.
- Ensuring that the Sponsor has received all required documentation, including but not limited to the signed Clinical Trial Agreement and IRB approvals.
- Appropriate procedures are followed to maintain subject confidentiality according to the Health Insurance Portability and Accountability Act (HIPAA) regulations. Each site may have its own internal procedures or requirements for use and release of subject medical information in research studies. Each Investigator is responsible for obtaining appropriate approvals, consents, or releases of medical information as dictated by their site's relevant patient privacy laws.
- The study is not transferable to other sites attended by the Principal Investigator unless prior approval is obtained from the appropriate IRB and the Sponsor.

- All records pertaining to this study will be kept for a minimum of two (2) years following the date on which the study is completed or terminated. If an Investigator wishes to withdraw from the responsibility for keeping the study records, custody per written notice must be submitted to the Sponsor, or designee, indicating the name and address of the person accepting primary responsibility. The IRB must also be notified in writing of the name and address of the new custodian.

## 23.3 Investigator Records and Reports

### 23.3.1 Investigator Records

Investigator is responsible for preparing and/or retaining the following records:

- Subject's case history records, including: signed/dated ICF, observations of adverse events, relevant medical history, results of tests and/or exams performed in this study, and dates and data collected at office visits and telephone follow-up;
- Protocol and any amendments; and
- IRB approval documents and related correspondence.

[Redacted]	[Redacted]	[Redacted]

## 24.0 Confidentiality

All records identifying the subject will be kept confidential and, to the extent permitted by the applicable laws and/or regulations, will not be made publicly available. Subject names will not be supplied to the Sponsor. Only the subject number will be recorded in the eCRF, and if the subject name appears on any other document (e.g. source document), it must be de-identified before a copy of the document is supplied to the Sponsor. Trial findings stored on a computer will be stored in accordance with local data protection laws. As part of the informed consent process, the subjects will be informed in writing that representatives of the Sponsor, IRB, or regulatory authorities may inspect their medical records to verify the information collected, and that all personal information made available for inspection will be handled in strictest confidence and in accordance with local data protection laws. If the results of the trial are published, the

subject's identity will remain confidential. The Investigator will maintain an onsite listing to enable subjects to be identified.

## **25.0 Regulatory Adherence**

The trial will be adhering to 21 CFR parts 50, 56, 803 and ISO 14155 Serious Adverse Event (SAE) reporting throughout the duration of the trial.

## **26.0 Use of Information and Publication**

Publication of data from this trial will be in accordance with the clinical trial agreements fully executed with Investigators and the Steering Committee Charter. All information and data relating to the clinical trial are the sole property of CSI. The Sponsor reserves the right to review and approve all publications and presentations utilizing the trial data.

For publication purposes, this trial will be submitted for inclusion in the clinical trial registry at: <http://www.ClinicalTrials.gov>.

1. INTRODUCTION

This statistical analysis plan (SAP) describes the statistical methods to be used during the reporting and analysis of clinical study data collected under study protocol [REDACTED], Radial accEss for nAvigation to your CHosen lesion for Peripheral Vascular Intervention (REACH PVI). This SAP should be read in conjunction with the study protocol and Case Report Forms (CRF). This version of the plan has been developed with respect to REACH PVI study protocol [REDACTED]. Any changes to this protocol or the CRFs may necessitate updates to the SAP.

2. STUDY OBJECTIVE

The objective of this study is to evaluate acute clinical results of orbital atherectomy (OA) via radial artery access, including complication rates and cost effectiveness.

2.1 Primary Outcome Measure: Procedural Success

Procedural success is defined as successful completion of OA treatment of the target lesion via transradial access (TRA) without serious transradial access related events.

2.2 Secondary Outcome Measure: Treatment Success

Treatment success is defined as <50% residual stenosis post-procedure and without significant angiographic complications without stent placement, or <30% residual stenosis post-procedure and without significant angiographic complications with stent placement.

3. STUDY DESIGN

This prospective, observational, single-arm, multi-center post-market clinical study is designed to prospectively evaluate acute clinical outcomes of OA via TRA for treatment of peripheral artery disease (PAD) in lower extremities

3.1 Enrollment

This study will enroll approximately (50) subjects at up to ten (10) active sites in the United States (US) who have signed an IRB-approved informed consent, have met all inclusion criteria and none of the exclusion criteria, and the ViperWire has been inserted into the body. For a full list of criteria for subject eligibility, refer to [REDACTED], section 9.0. Subjects found to not meet index inclusion criteria or to meet index exclusion criteria will be considered consented screen failures.

3.2 Duration

The duration of this study is expected to be approximately eight (8) months. Subjects will be followed post-procedure through the first standard of care follow-up visit (7-45 days post procedure) only.

3.3 Sample Size

As a hypothesis generating study, this study is not powered.

4

[figure not shown]

5. DATA ANALYSIS SETS

The Primary Analysis will be based on the Intent to Treat (ITT) analysis set, unless otherwise noted. The following analysis sets are specified for REACH PVI.

5.1 Intent to Treat (ITT) Analysis Set

The ITT analysis set will include all enrolled subjects who have been enrolled regardless of deviations from the protocol.

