## 8.0 Sample Size

Approximately 50 subjects treated with OA will be enrolled in this study. As a hypothesis generating study, this study is not powered.

Subjects must meet ALL of the inclusion criteria and NONE of the exclusion criteria to be eligible to participate in this study. Subject will be approached and consented for participation in the study prior to the index procedure, during which index inclusion and exclusion criteria will be confirmed. Subjects found to not meet index inclusion criteria or to meet index exclusion criteria will be considered consented screen failures.

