### **9.4 Index Procedure Exclusion Criteria**

1. Physician unable to obtain radial artery access
2. Physician determines TRA is not acceptable due to patient anatomy, lesion characteristics, and/or disease severity
3. OAS use not attempted (defined as ViperWire introduced into the body)

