**Prior to insertion of ViperWire:**

4. Femoral access is obtained
5. Unsuccessful peripheral intervention
6. A reportable adverse event has occurred

[figure not shown]

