7.4 Primary Outcome Measure Analysis

Analysis of the primary outcome measure of Procedural Success will be assessed post-procedure on the ITT analysis set. Procedural Success is comprised of:

- Successful completion of OA treatment via transradial access determined by use of the device within the target lesion
- The presence of no serious transradial access related events. TRA related events include:
 - Serious TRA site bleeding (BARC Type 2-5)
 - Serious TRA site hematoma
 - Serious radial artery spasm
 - Serious hand ischemia
 - Stroke
 - Transient Ischemic Attack (TIA)
 - Serious nerve damage
 - Perforation
 - TRA site pseudoaneurysm

Procedural Success is considered successful for a subject if all criteria are met.

A large rectangular area of the page is completely blacked out, indicating redacted content. It is positioned below the 'Procedural Success' text and above the page footer.

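### Eligibility is part of the definition of enrollment, yet ineligible enrollment is a deviation kept in ITT, and two untimed index criteria let a failed case be relabelled a screen failure after ViperWire insertion

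*SAP*

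**What the plan says.** Four provisions bear on who is in the ITT set.

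- **Analysis set.** SAP 5.1 includes "all enrolled subjects who have been enrolled regardless of deviations from the protocol". SAP 7.4 and 7.8 use this set for Procedural Success and for AE rates, and Protocol 7.0 ties both outcomes to enrolled subjects.
- **Enrollment.** SAP 3.1 describes enrolled subjects as those who have signed consent, "have met all inclusion criteria and none of the exclusion criteria, and the ViperWire has been inserted into the body". Protocol 9.6 sets the same three conditions.
- **Screen failure.** Protocol 8.0, repeated in SAP 3.1, states: "Subjects found to not meet index inclusion criteria or to meet index exclusion criteria will be considered consented screen failures". Protocol 8.0 also says that consent is taken "prior to the index procedure, during which index inclusion and exclusion criteria will be confirmed".
- **Deviations.** Protocol 15.0 lists as a reportable deviation: "Enrolling a subject who did not meet inclusion criteria, or met exclusion criteria".

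Protocol 9.4 places index exclusions 4 to 6 under the limit "Prior to insertion of ViperWire". Index exclusion 2 sits above that limit and reads: "Physician determines TRA is not acceptable due to patient anatomy, lesion characteristics, and/or disease severity". Index inclusion 2 in Protocol 9.2, on whether the lesion suits OA from the radial approach, also has no time limit.

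**The concern.** If eligibility is a condition of being enrolled, nobody can be enrolled while ineligible, and the deviation in Protocol 15.0 could never occur. If that deviation can occur, eligibility is not strictly a condition of enrollment. The two pairs of provisions give opposite answers for a subject who has the wire in place and is then judged ineligible, and no readable sentence says which prevails.

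The screen-failure rule makes this more than a matter of drafting. It contains no statement that the determination must precede wire insertion, and two of the criteria it covers are physician judgements closely tied to the primary outcome. A judgement that radial access or the lesion was unsuitable can be prompted by the same difficulty that stops the device from being used. The label would then be chosen with the result known, in a single-arm study with no comparator in which the shift might show. AE collection starts at enrollment (Protocol 13.1, SAP 7.8), so a subject reclassified as never enrolled could also take complications out of the AE tables.

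**Working it through.** **Step 1: which index criteria remain open after wire insertion?**

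| Index criterion | Status once the ViperWire is in |
|---|---|
| Inclusion 1 / exclusion 1 (radial access obtained) | Settled |
| Inclusion 3 / exclusion 3 (OAS attempted, defined by wire introduction) | Settled by insertion itself |
| Exclusions 4, 5, 6 (femoral access, unsuccessful intervention, reportable AE) | Expressly limited to the period before insertion |
| Exclusion 2 (radial access not acceptable) | No time limit; physician judgement |
| Inclusion 2 (lesion suitable for radial OA) | No time limit; physician judgement |

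The open route is therefore exclusion 2 and inclusion 2. General criteria (Protocol 9.1 and 9.3) are outside the screen-failure rule, which names index criteria only.

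**Step 2: trace one subject.** Consent is signed, radial access is obtained and the ViperWire is inserted, but the device cannot be used in the lesion. The physician then concludes that the anatomy or lesion made radial access unacceptable.

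- SAP 7.4 requires "Successful completion of OA treatment via transradial access determined by use of the device within the target lesion". The subject does not meet this and is a Procedural Success failure.
- Protocol 15.0 with SAP 5.1: ineligible enrollment is a deviation, deviators are kept, and the subject counts as a failure in the denominator.
- Protocol 9.6 and SAP 3.1 with the screen-failure rule, read literally: an index exclusion is met, so the subject is a screen failure, is not enrolled and is not in the denominator.

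Both readings use stated text.

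**Step 3: scale.** The plan gives no figure to reproduce: the study is declared unpowered and the target of about 50 has no derivation. The counts below are assumptions. Let 50 subjects have the wire inserted, k failures be relabelled and m other failures remain.

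- Kept: (50 − m − k)/50
- Dropped: (50 − m − k)/(50 − k)
- Gain: (50 − m − k) × k / [50 × (50 − k)]

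With m = 2 and exact (Clopper-Pearson) 95% intervals (SAP 6.2 gives alpha 0.05; the interval method is assumed):

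| k | Kept | Dropped | Gain (points) |
|---|---|---|---|
| 1 | 47/50 = 94.0% (83.5–98.7) | 47/49 = 95.9% (86.0–99.5) | 1.9 |
| 3 | 45/50 = 90.0% (78.2–96.7) | 45/47 = 95.7% (85.5–99.5) | 5.7 |
| 5 | 43/50 = 86.0% (73.3–94.2) | 43/45 = 95.6% (84.9–99.5) | 9.6 |

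Check for k = 3: 45 × 3 / (50 × 47) = 135/2350 = 0.057. Across m = 0 to 5 the gain is 1.8–2.0 points for k = 1, 5.4–6.0 for k = 3 and 8.9–10.0 for k = 5, or about 2 points per relabelled failure.

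**The case against.** The best defence is that the documents already answer the question. Protocol 15.0 accepts that an ineligible subject can be enrolled, and SAP 5.1 keeps enrolled subjects whatever the deviation. Read together they favour retention, and the opposite reading leaves the listed deviation with nothing to apply to. Protocol 8.0 has index criteria confirmed during the procedure, Protocol 9.6 treats enrollment as a point in time, and AE reporting starts straight after it, so status seems meant to be fixed as the case proceeds. The time limit on exclusions 4 to 6 also closes the most obvious routes: femoral crossover, failed intervention or an AE after insertion does not exclude anyone.

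Most of this stands, and it limits the point. A reader might infer that any subject later found ineligible, on a general or an index criterion, becomes a screen failure and drops out of ITT. The documents do not support that: the screen-failure rule does not reach general criteria, and no rule directs the removal of an enrolled subject. A general-criterion failure found late still meets the conflict between the enrollment definition and the deviation list, but no stated relabelling route.

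The defence does not close the gap for exclusion 2 and inclusion 2. Confirmation during the procedure is not confirmation before wire insertion, because the procedure continues after it. That exclusions 4 to 6 carry an explicit limit makes its absence from exclusion 2 more noticeable.

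The defence is also right that the counts are invented, that relabelling only failures is the unfavourable direction, and that the intervals overlap widely. Lack of power is a weaker reply, since the observed rate is the main product of a descriptive study.

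**Conclusion.** The point holds as an unresolved inconsistency with one narrow, outcome-linked route, and should be corrected. Protocol 9.6 and SAP 3.1 must be reconciled with Protocol 15.0 and SAP 5.1. Until they are, a wire-inserted subject judged after insertion to fail index exclusion 2 or inclusion 2 can be treated as a retained failure or as a screen failure.

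The size is about 2 percentage points of observed Procedural Success per relabelled failure. This assumes 50 wire-inserted subjects and that those relabelled are failures; the documents give no expected number. The same subjects would leave the Treatment Success and AE denominators.

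Two further inferences go too far. One is that the plan sets out to drop difficult cases: its clearest statement of intent, SAP 5.1, points the other way. The other is that ITT is certainly the only analysis set. It is the only one in the readable text, but SAP 5 speaks of sets in the plural, and parts of both documents, including the deviation list, are redacted. A clarifying rule may exist there.

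**What to change.** 1. In SAP 5.1, define the ITT set as all subjects with signed consent and the ViperWire inserted, irrespective of any eligibility violation found later. Bring Protocol 9.6 and SAP 3.1 into line, so that eligibility is required of sites but does not decide whether a wire-inserted subject counts as enrolled.
2. In Protocol 8.0 and SAP 3.1, limit the consented screen-failure category to determinations made and recorded before ViperWire insertion.
3. Report ineligibility found after insertion as a protocol deviation, with counts and reasons in the disposition summary (SAP 7.1).

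This is a wording change in a few places. It needs no added data and leaves clinical decisions untouched. The cost is that a few ineligible subjects stay in the analysis, which SAP 5.1 already intends. If redacted text already contains such a rule, a cross-reference from these sections would be enough.

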6. DATA ANALYSIS METHODOLOGY & CONVENTIONS

The primary analysis of REACH PVI subjects will be based on archived clinical data and the ITT analysis set unless otherwise noted.

Statistical analyses will be performed using SAS® software (SAS Institute Inc., [name], USA). In the event an analysis is required that is better suited for a statistical package other than SAS (e.g., SPSS, R), the other package may be used.

[figure not shown]
6.1 Timing of Analysis

Analyses of all primary and secondary outcome measures will be performed after all ITT subjects have a completed end of study (EOS) CRF, all queries have been resolved, and the physician has signed all subject CRFs.

6.2 Analysis Conventions

This section details the general conventions to be used for data analysis. Departures from these general conventions may be given in the specific detailed sections of this SAP. When this occurs, the rules set forth in the specific section take precedence over the general conventions. Departures from the plans laid out in this document will be explained and justified with appropriate scientific, clinical and/or statistical justification.

- Data will be summarized for the ITT analysis set unless otherwise noted
- Continuous variables will be summarized using mean, standard deviation (SD), median, quartiles, minimum, and maximum and the number of subjects with non-missing data
- Categorical and discrete variables will be summarized by the number and percent of responses in each category and rounded to a single decimal point
- Unless otherwise specified missing data will be excluded from the denominator
- Confidence intervals will use an alpha level of 0.05
- If required for an analysis, partial dates will be completed by imputing the date using the most conservative approach for that specific date
- All listings will be sorted for presentation in order of site, subject number, and the date-time of the procedure or event (when applicable)
- Outcomes examining the standard-of-care (SOC) follow-up visit will be presented as binomial outcomes with the denominator equal to the number of patients with the SOC follow-up visit.

6.4 Analysis Windows

Assessments will be made at baseline (\leq 30 days prior to procedure), pre-procedure (\leq 24 hours prior to procedure), during the procedure, and post-procedure/discharge. A standard-of-care in-office follow-up visit is scheduled at 7-45 days post-procedure. All intervals will be calculated in days (e.g., 1-month will be calculated as 30 days).

7. REQUIRED DATA ANALYSES

The following analyses will be performed on the ITT population unless otherwise noted. Analyses will occur on the target lesion, defined as the stenotic segment appropriate for treatment with the Orbital Atherectomy System study device(s) via transradial access. The target lesion will be:

- The first lesion with Orbital Atherectomy attempted OR
- The first lesion with Orbital Atherectomy attempted after other successful peripheral intervention(s) without the occurrence of a reportable adverse event.

The study will be limited to one (1) target lesion per enrolled subject.

